1.0 Objectives*

Alcohol intake raises sex hormone levels, however, it is unknown if that effect persists in postmenopausal women with estrogen receptor-positive (ER+) breast cancer on aromatase inhibitor (AI) therapy, which is an estrogen suppressant. There have been no studies to examine alcohol's effect on sex hormone levels among postmenopausal women with ER+ breast cancer receiving AI therapy. These drugs are only prescribed to postmenopausal women who had ER+ breast cancer, the subtype where alcohol has been found to increase breast cancer incidence. This information is needed for postmenopausal women with estrogen receptor-positive (ER+) breast cancer to make informed decisions about their alcohol intake and its potential effect on adjuvant AI therapy.

To address this issue, we will conduct a pilot randomized controlled crossover trial of 20 postmenopausal women with estrogen receptor-positive (ER+) breast cancer who receive AI therapy and who consume at least one alcoholic drink per week but not more than one drink per day, to assess whether alcohol at low "real-world" levels of intake increases sex hormone levels in the presence of AI's.

We hypothesize that the expected within-person increases in sex hormone levels following light alcohol consumption will not be observed among women using aromatase inhibitor therapy throughout study enrollment.

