3.0 Inclusion and Exclusion Criteria*

We aim to identify postmenopausal women with estrogen receptor-positive (ER+) breast cancer who typically consume at least one alcoholic drink per week but not more than two servings per day and are currently prescribed aromatase inhibitors including anastrozole (Arimidex®), letrozole (Femara®), and exemestane (Aromasin®). These drugs are only prescribed to postmenopausal women who have been diagnosed with estrogen receptor positive (ER+) breast cancer, the subtype where alcohol has been found to increase breast cancer incidence.

Inclusion Criteria:

- ER+ breast cancer
- Female sex at birth
- Postmenopausal, either natural or induced
- Self-reported consumption of at least one alcoholic drink per week but not more than two servings per day
- Currently prescribed aromatase inhibitors including anastrozole (Arimidex®), letrozole (Femara®), and exemestane (Aromasin®)
- Documented liver function test results below 1.5X the upper limit of normal within 12 months of screening

Exclusion criteria:

- Self-reported consumption of more than two drinks per day, a previous or current history of alcohol abuse based on standard questionnaires (AUDIT \geq 8), or consumption of 4 or more drinks in one day within the last 6 months
- Currently undergoing cytotoxic chemotherapy or radiation planned in the next two months
- Any surgery planned in the next two months
- Alcohol flushing syndrome
- Current use of any pharmaceutical agent contraindicated with alcohol, including warfarin, dual antiplatelet therapy, and metronidazole
- Hemoglobin A1c $>$ 8% or a fasting glucose result above 180 mg/dL within 6 months of screening

- Unable to speak or understand English
- Unable to understand and provide informed consent, as judged by the study team
- Uncertain ability to complete the protocol, as judged by the study team

We will not include adults unable to consent, individuals who are not yet adults, pregnant women, or prisoners.

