9.0 Procedures Involved*

This is an unblinded randomized controlled crossover trial to examine whether 3 weeks of light alcohol consumption causes a short-term change in sex hormone levels compared to levels following 3 weeks of white grape juice consumption among postmenopausal women with estrogen receptor-positive (ER+) breast cancer taking an aromatase inhibitor. In this design, participants are compared to themselves at different times, with the sequence of the two treatment arms assigned by randomization. In other words, half of the women will be randomized to consume one serving of white wine every day for three weeks followed by one serving of white grape juice every day for three weeks, and half of the women will be randomized to three weeks of white grape juice followed by three weeks of white wine. To prevent a potential carryover effect of the drink in the first period affecting hormone levels in the second treatment period, we will ask participants to refrain from drinking any alcohol or grape juice for two weeks before starting each treatment arm. The women will know when they are supposed to drink the wine and when they are supposed to drink the grape juice.

Recruitment:

We will present the trial protocol and eligibility criteria at a meeting for the six medical oncologists and three nurse practitioners who provide outpatient care at the BIDMC BreastCare Center and ask for their assistance to recruit patients from their practice who may be eligible and interested in participating in our trial.

We will review medical records for patients receiving care in the BreastCare Center or Healthcare Associates (HCA), BIDMC's primary care practice, to see if they meet the eligibility criteria, and contact their health provider about their fitness to participate. Unless their provider recommends otherwise, we will mail an invitation letter to patients who appear to be eligible and ask them to contact us if interested. If they do so and remain interested, we will arrange a screening visit. We will also call participants who have received letters and have upcoming clinical appointments to remind them of the study and to determine if they would like to arrange a screening visit in conjunction with that appointment. We will also continue to place flyers and brochures in the BreastCare Center so that women who are interested in the study can reach out to us.

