11.0 Data Management* and Confidentiality

We will present descriptive statistics on the proportion of people screened who were eligible and ineligible, and the number randomized. We will describe the health characteristics and self-reported adherence of the completers and non-completers based on the available data.

We will construct linear mixed models to examine within-person changes in levels of estradiol, testosterone, DHEAS, and SHBG from grape juice to white wine, including a random subject intercept and fixed effects for treatment and sequence. We will assess the potential for a carryover effect by evaluating a cross-product term for treatment and sequence. We will use a logarithmic transformation for skewed distributions of the sex hormone levels.

We will use Markov Chain Monte Carlo (MCMC) multiple imputation. For each treatment arm, we will use the SAS “proc mi” procedure to generate 10 multiply imputed datasets that incorporate appropriate variability across the imputations. We will use the SAS “proc mianalyze” procedure to combine the results from the imputed data sets to properly reflect the uncertainty due to missing values.

Our primary analysis will use an intention-to-treat (ITT) approach, classifying participants according to their assigned treatment arms regardless of adherence to study protocol. In a sensitivity analysis, we will use a per-protocol approach in which a participant’s follow-up will be terminated at the time, if any, at which they cease to follow the protocol, and we will adjust for pre-randomization and post-randomization factors that may predict adherence.

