Our primary endpoint is free estradiol (estradiol divided by SHBG). We should have excellent power to assess effects of alcohol on DHEAS but reasonable power to detect effects on estrone sulfate, although, as a pilot study with an intentional goal of training and career development, power is but one dimension on which to evaluate the merits of the trial. We have used standard formulae to estimate the minimum detectable difference for 2-period crossover trials (http://hedwig.mgh.harvard.edu/sample_size/js/js_crossover_quant.html). Using the 4-week results of a similar crossover trial of alcohol on changes in estrone sulfate and DHEAS, and using the dosage of 15 gm/day that most closely approximates the dosage proposed in this application, we can estimate the proportional changes anticipated with varying degrees of power, as shown below at a two-sided 0.05 significance level. Based upon data presented in that trial, we estimate the SD of within-person differences to be 42% for estrone sulfate and 13% for DHEAS.

Power	Minimum Detectable Difference	
	Estrone sulfate (ng/dl)	DHEAS (ng/dl)
50%	19%	6%
80%	28%	9%
90%	32%	10%

For comparison, the increases in estrone sulfate in previous trials of alcohol were 15-21% in a trial of premenopausal women and 7-22% in a trial of postmenopausal women.

The comparable effects on DHEAS were 4-7% and 5-9%. Thus, we appear to have adequate power to detect effects of the expected size from previous crossover trials. Moreover, we have particularly strong power to exclude virtually all clinically significant increases (e.g., increases of 10% or larger) in DHEAS.

Our results would also provide all necessary information to power a more definitive trial of estrone and other estrogens.

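### The hypothesis predicts no hormone rise on AI therapy, but the plan has no rule for concluding absence on its primary endpoint, and its power claim does not fit its own table

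*Combined protocol and SAP*

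**What the plan says.** Section 1.0 gives an objective and a hypothesis. The objective is to assess whether low alcohol intake raises sex hormones in women on an aromatase inhibitor (AI). The hypothesis is that "the expected within-person increases in sex hormone levels following light alcohol consumption will not be observed among women using aromatase inhibitor therapy". Section 9.0 describes the trial as one "to examine whether 3 weeks of light alcohol consumption causes a short-term change in sex hormone levels" compared with grape juice. Section 3.0 requires every participant to be "currently prescribed aromatase inhibitors including anastrozole" or another AI.

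Section 11.0 states: "We will construct linear mixed models to examine within-person changes in levels of estradiol, testosterone, DHEAS, and SHBG from grape juice to white wine". It names no test, decision rule or confidence-interval criterion. The power text in the same section says "Our primary endpoint is free estradiol (estradiol divided by SHBG" but gives no SD, prior effect or power for it, and free estradiol is not in the list of modelled outcomes.

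The power table covers estrone sulfate and DHEAS, "as shown below at a two-sided 0.05 significance level". Minimum detectable differences at 50%, 80% and 90% power are 19%, 28% and 32% for estrone sulfate, and 6%, 9% and 10% for DHEAS. Prior effects cited for estrone sulfate are 15-21% (premenopausal) and 7-22% (postmenopausal). For DHEAS, "The comparable effects on DHEAS were 4-7% and 5-9" per cent. The text then concludes that "we appear to have adequate power to detect effects of the expected size from previous crossover trials", and adds that power is particularly strong to exclude clinically significant DHEAS increases, with 10% or larger as the example.

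**The concern.** A hypothesis worded as something not being observed is satisfied most easily by a non-significant p-value. When the plan also says that power is adequate for the expected effect, a reader has been told in advance that non-significance is informative. With 20 women it may not be.

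Sections 1.0 and 2.0 say that women on AI therapy need this information to decide about drinking. The costly error is therefore to report that the rise is not seen on AI therapy when the usual rise is fully present.

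**Working it through.** **Inputs.** N = 20 completers (Section 23.0). SD of within-person differences is 13% for DHEAS and 42% for estrone sulfate, with two-sided alpha 0.05 (Section 11.0). A two-sequence, two-period crossover gives 18 df, so t(0.975, 18) = 2.101. Percentages are treated as additive (assumption, checked below).

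**Standard errors and half-widths.** SE = SD/√20.
- DHEAS: 13/4.472 = 2.907 points; 95% half-width 2.101 × 2.907 = 6.11 points.
- Estrone sulfate: 42/4.472 = 9.391 points; half-width 2.101 × 9.391 = 19.73 points.

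**The plan's table.** Solving noncentral-t power for the difference at 50%, 80% and 90% gives 6.0, 8.6 and 10.0% for DHEAS and 19.4, 27.8 and 32.2% for estrone sulfate. These match the table after rounding.

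**Power at the cited effects.** Power = P(|T| > 2.101), where T is noncentral t with 18 df and noncentrality δ/SE.

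| Hormone | True rise δ | δ/SE | Power | Non-significant |
|---|---|---|---|---|
| DHEAS | 4% | 1.376 | 26% | 74% |
| DHEAS | 5% | 1.720 | 37% | 63% |
| DHEAS | 7% | 2.408 | 62% | 38% |
| DHEAS | 9% | 3.096 | 83% | 17% |
| Estrone sulfate | 7% | 0.745 | 11% | 89% |
| Estrone sulfate | 15% | 1.597 | 33% | 67% |
| Estrone sulfate | 21% | 2.236 | 56% | 44% |
| Estrone sulfate | 22% | 2.343 | 60% | 40% |

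For DHEAS, 80% power is reached only at the top of the cited range. For estrone sulfate it needs 28%, above every cited effect. If the two DHEAS ranges keep the order of the preceding sentence, the postmenopausal range is 5-9%, with power 37-83%.

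**Scale check.** On a log scale with SD ln(1.13) = 0.122 or 0.13, the DHEAS non-significance rates at 4, 5, 7 and 9% are 73-75%, 61-64%, 35-40% and 15-20%. The additive assumption hardly matters.

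**The 10% remark.** If the true effect is zero, the chance that the upper 95% limit falls below m is P(T < -2.101) with noncentrality -m/SE. For DHEAS at m = 10% this is 90%, so the remark is numerically right. At 9, 7, 5 and 4% it is 83%, 62%, 37% and 26%. The 10% figure lies above the whole cited range of 4-9%, so excluding it is compatible with the full usual rise.

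**Error rate of an interval rule.** If a prior effect persists in full, the upper 95% limit falls below it in 2.5% of trials, whatever its size.

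**Free estradiol.** No calculation is possible, because the plan gives no SD and no effect size.

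**The case against.** The strongest reply is that the objective in Section 1.0, repeated in Section 2.0, asks whether alcohol raises hormones on AI therapy. The mixed model answers that question. Only the single hypothesis sentence speaks of absence. The trial is called a pilot, Section 11.0 says power is only one dimension of its merit, and the results are meant to help size a more definitive trial. This stands: objective and analysis agree, and the gap lies between the hypothesis and the rules for reading the result.

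Some stronger readings are tempting but not supported:

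- A reader might infer that the plan says nothing at all about absence. It does name a DHEAS size to exclude, with correct power. That remark is an example for a non-primary hormone and is not carried into the analysis text.
- A reader might infer that the investigators intend to treat non-significance as proof of absence. No section says so; the plan leaves that reading open.
- A reader might put a precision on free estradiol by borrowing the SDs of 13% and 42%. Nothing in the documents shows that the SD of this ratio, in women on an estrogen suppressant, lies between them.

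It can also be said that the adequate-power sentence follows the DHEAS figures and refers only to them. Even so, 80% power is reached only at the top of that range.

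**Conclusion.** The point holds in this form. The hypothesis predicts absence, and apart from the 10% DHEAS remark the plan gives no confidence-interval rule for concluding it, and none for the primary endpoint. The claim of adequate power for effects of the expected size is wrong on the plan's own table: power is 26-83% for DHEAS and 11-60% for estrone sulfate. A fully persisting effect would give a non-significant result in 17-74% and 40-89% of trials respectively, so non-significance cannot support the hypothesis.

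These figures assume 20 completers and that the SDs and effects from the earlier trials carry over to women on AI therapy. Section 2.0 says no such study exists, so this is untested. They concern the two hormones that the plan sized, neither of which is the primary endpoint.

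A minor related point: the stopping text in Section 12.0 says the trial tests whether AI use reduces the effect of alcohol. Every participant takes an AI, so that can only be a comparison with historical data. The sentence is not part of the analysis plan.

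**What to change.** In Section 11.0:

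1. Replace the adequate-power sentence with the power figures above for both hormones, and say that no SD or power is available for free estradiol.
2. Add free estradiol to the modelled outcomes. Report each hormone's wine-juice effect with a two-sided 95% CI: as a ratio where the outcome is log-transformed, otherwise as a difference, also expressed as a percentage of the juice mean.
3. State that a non-significant result does not support the hypothesis. A cited prior effect is called excluded only if it lies above the upper 95% limit; otherwise the result is inconclusive for that size. The usual DHEAS rise is called absent only if the lowest cited effect, 4%, is excluded.
4. Present free estradiol as estimation only, unless a size to exclude is written in before the assays are run. This is practicable, because the hormone samples are stored until all participants finish.

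Optionally, label the Section 12.0 statement as a historical comparison.

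**Cost.** Data collection and sample size do not change, and one model is added. The real price is that many results will be inconclusive. Even with a true effect of zero, 20 women exclude the 4% DHEAS rise only 26% of the time; an 80% chance would need about 85 women under the same assumptions. That limit already exists, and the change only makes it visible.

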2.0 Background*

Several controlled feeding studies among premenopausal and postmenopausal women showed that alcohol supplementation for a few weeks acutely increases estrogen and sex hormone-binding globulin (SHBG) levels. However, data on how light intake of alcohol impacts sex hormone levels among women receiving estrogen suppressants is critical for guiding postmenopausal women with estrogen receptor-positive (ER+) breast cancer about the safety of alcohol intake.

In a cross-sectional study of 490 postmenopausal breast cancer survivors (Wayne S. *Cancer Epidemiol Biomarkers Prev.* 2008;17(11):3224-3232.), alcohol intake and sex hormone levels were strongly associated despite the relatively low range of alcohol intake in study participants. Tamoxifen use dampened the association between alcohol intake and dehydroepiandrosterone sulfate (DHEAS) levels, and among participants with ER+ tumors, there was no association between alcohol intake and sex hormone-binding globulin (SHBG).

Although alcohol intake raises sex hormone levels, it is unknown if that effect persists on aromatase inhibitor therapy, in part because the mechanism underlying alcohol's effect on sex hormone levels is not well understood. Despite the potential

risks of alcohol intake on hormone levels, a cancer diagnosis is not associated with long-term changes in daily alcohol intake. Furthermore, there have been discrepant findings on the association between alcohol intake and breast cancer recurrence and survival. Some studies have found that alcohol intake is not associated with a higher rate of breast cancer mortality, and it may even lower the rate of all-cause mortality.

There have been no studies to examine alcohol's effect on sex hormone levels among postmenopausal women with estrogen receptor-positive (ER+) breast cancer receiving aromatase inhibitor therapy. This information is needed for them to make informed decisions about their alcohol intake and its potential effect on adjuvant aromatase inhibitor therapy. Therefore, we will conduct a pilot randomized controlled crossover trial to assess whether alcohol at low "real-world" levels of intake increases sex hormone levels in the presence of aromatase inhibitor therapy.

3.0 Inclusion and Exclusion Criteria*

We aim to identify postmenopausal women with estrogen receptor-positive (ER+) breast cancer who typically consume at least one alcoholic drink per week but not more than two servings per day and are currently prescribed aromatase inhibitors including anastrozole (Arimidex®), letrozole (Femara®), and exemestane (Aromasin®). These drugs are only prescribed to postmenopausal women who have been diagnosed with estrogen receptor positive (ER+) breast cancer, the subtype where alcohol has been found to increase breast cancer incidence.

Inclusion Criteria:

- ER+ breast cancer
- Female sex at birth
- Postmenopausal, either natural or induced
- Self-reported consumption of at least one alcoholic drink per week but not more than two servings per day
- Currently prescribed aromatase inhibitors including anastrozole (Arimidex®), letrozole (Femara®), and exemestane (Aromasin®)
- Documented liver function test results below 1.5X the upper limit of normal within 12 months of screening

Exclusion criteria:

- Self-reported consumption of more than two drinks per day, a previous or current history of alcohol abuse based on standard questionnaires (AUDIT \geq 8), or consumption of 4 or more drinks in one day within the last 6 months
- Currently undergoing cytotoxic chemotherapy or radiation planned in the next two months
- Any surgery planned in the next two months
- Alcohol flushing syndrome
- Current use of any pharmaceutical agent contraindicated with alcohol, including warfarin, dual antiplatelet therapy, and metronidazole
- Hemoglobin A1c $>$ 8% or a fasting glucose result above 180 mg/dL within 6 months of screening

- Unable to speak or understand English
- Unable to understand and provide informed consent, as judged by the study team
- Uncertain ability to complete the protocol, as judged by the study team

We will not include adults unable to consent, individuals who are not yet adults, pregnant women, or prisoners.

4.0 Study-Wide Number of Subjects*

Not Applicable. This is a single-site pilot trial.

5.0 Study-Wide Recruitment Methods*

Not Applicable. This is a single-site pilot trial.

This pilot study is funded by very limited project funds from [name] K01 award and comprises a total of 20 women – a small enough total to be readily completed at a single center. [name], a research collaborator at BIDMC, will conduct recruitment herself at the BI oncology clinics. As a result, expansion beyond BIDMC is not currently feasible on the project's NIH-funded budget.

6.0 Multi-Site Research*

Not Applicable. This is a single-site pilot trial.

7.0 Study Timelines*

- Each participant will be involved in the study for ten weeks from the date of her screening visit.
- We anticipate that it will take one year from the date of IRB approval to recruit and enroll enough women so that 20 women will have completed all study visits.
- We anticipate that it will take 2 years from the date of IRB approval to complete the interviews, clean the data and prepare the primary analyses.

8.0 Study Endpoints*

We will examine within-person changes in blood levels of estradiol, testosterone, dehydroepiandrosterone sulfate (DHEAS), and sex hormone-binding globulin (SHBG) after three weeks of one serving of white wine daily compared to levels after three weeks of one serving of white grape juice daily.

At visits 1, 2, 3, and 4, the BIDMC Clinical Research Center (CRC) nurses will obtain a fasting blood sample. Within 72 hours, Quest Diagnostics will measure hepatic function, a complete blood count, and following visits 2 and 4, they will conduct a lipid panel. On our weekly phone check-ins, we will ask about recent health events such as unscheduled hospitalizations or any symptoms that have developed since the last meeting.

